7.3. Body Weight and Vital Signs

Descriptive statistics will be provided by treatment group for body weight, BMI and vital signs (systolic and diastolic blood pressures [mmHg], pulse [beats/min]) as follows:

- Filgotinib baseline value
- Values at each postbaseline visit
- Change from filgotinib baseline at each postbaseline visit

A filgotinib baseline value will be defined as the last available value collected on or prior to the date/time of first dose of filgotinib in the core studies or GLPG0634-CL-205. Change from filgotinib baseline to a postbaseline visit will be defined as the postbaseline value minus the filgotinib baseline value. Body weight and vital signs measured at unscheduled visits will be included for the filgotinib baseline value selection.

In the case of multiple values in an analysis window, data will be selected for analysis as described in Section 3.5.3. No formal statistical testing is planned.

A by-subject listing of vital signs (systolic and diastolic blood pressure [mmHg], pulse [beats/min]) will be provided by subject ID number and visit in chronological order. In the same manner, a by-subject listing of body weight, height, and BMI will be provided separately.

7.4. Concomitant Medications

Medications collected during the study will be coded using the World Health Organization (WHO) Drug dictionary version BSEP17.

Concomitant medications are defined as medications taken while a subject took study drug in GLPG0634-CL-205. Use of concomitant medications will be summarized by ATC drug class preferred name using the number and percentage of subjects for each treatment group. A subject reporting the same medication more than once will be counted only once when calculating the number and percentage of subjects who received that medication. The summary will be provided by preferred name in descending overall frequency. For drugs with the same frequency, sorting will be done alphabetically.

For the purposes of analysis, any medication with a start date prior to or on the first dosing date of filgotinib in GLPG0634-CL-205 and continued to take after the first dosing date, or started after the first dosing date but prior to or on the last dosing date of filgotinib in GLPG0634-CL-205 will be considered concomitant medications. Medications started and stopped on the same day as the first dosing date or the last dosing date of filgotinib in GLPG0634-CL-205 will also be considered concomitant. Medications stopped on the same day as the first dosing date of filgotinib in GLPG0634-CL-205 will be considered concomitant. Medications with a stop date prior to the date of first dosing date of filgotinib in GLPG0634-CL-205 or a start date after the last dosing date of filgotinib in GLPG0634-CL-205 will be excluded from the concomitant medication summary. If a partial stop date is entered, any medication with the month and year (if day is missing) or year (if day and month are missing) prior to the date of first filgotinib administration in GLPG0634-CL-205 will be excluded from the concomitant medication summary. If a partial start date is entered, any medication with the month and year (if day is missing) or year (if day and month are missing) after the filgotinib stop date in GLPG0634-CL-205 will be excluded from the concomitant medication summary. GLPG0634-CL-205 medications with completely missing start and stop dates will be included in the concomitant medication summary, unless otherwise specified.

Summaries will be based on the Safety Analysis Set. No formal statistical testing is planned.

All GLPG0634-CL-205 concomitant medications (other than per-protocol study drugs) will be provided in a by-subject listing sorted by subject ID number and administration date in chronological order.

7.5. Electrocardiogram Results

7.5.1. Investigator Electrocardiogram Assessment

A shift table of the investigators' assessment of ECG results at each visit compared with filgotinib baseline values will be presented by treatment group using the following categories: normal; abnormal (not clinically significant); abnormal (clinically significant); or missing. The number and percentage of subjects in each cross-classification group of the shift table will be presented. Subjects with a missing value at filgotinib baseline or postbaseline will not be included in the denominator for percentage calculation.

No formal statistical testing is planned.

A by-subject listing for ECG assessment results will be provided by subject ID number and visit in chronological order.

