8.9.1.3 Safety Variables

Clinical safety will be evaluated by assessing treatment-emergent AEs (TEAEs), physical examinations, laboratory assessments, ECG results, and vital signs results. The safety analysis may combine the data of all 3 studies (GLPG0634-CL-203, GLPG0634-CL-204, and GLPG0634-CL-205).

A treatment-emergent analysis of AEs will be done, based on the start date of the AE. TEAE (AE and SAE) preferred terms, intensity, frequency, relationship to study medication, dose reductions, and temporary/permanent treatment stops will all be tabulated. An additional analysis based on patient-years of exposure may be added when deemed useful.

Original results and changes from baseline will be summarized for all laboratory, vital signs, and ECG parameters, intended to detect any changes in safety parameters that could be attributed to GLPG0634 dosing. No imputations will be done for safety data in cases where subjects discontinued the study prematurely.

Further subgroup analyses (e.g., a selection of TEAEs with an onset date during the first weeks or months, or a division according to the mean actual dose) and exploratory analyses may be added when deemed appropriate.

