If multiple valid, nonmissing, categorical measurements exist in an analysis window, records will be chosen based on the following rules if a single value is needed:

- For filgotinib baseline, the last available record on or prior to the date of the first dose of filgotinib in the core studies or GLPG0634-CL-205 will be selected. If there are multiple records with the same time or no time recorded on the same day, the value with the lowest severity will be selected (eg, normal will be selected over abnormal for safety ECG findings).

- For postbaseline visits:
 - The record closest to the nominal day for that visit will be selected.
 - If there are 2 records that are equidistant from the nominal day, the later record will be selected.
 - If there is more than 1 record on the selected day, the value with the worst severity will be selected (eg, abnormal will be selected over normal for safety ECG findings), unless otherwise specified.

The rules for selecting efficacy data in the event of multiple records in an analysis visit window are specified in Section [6.1](#).

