7.2.2.3. Summaries of Laboratory Abnormalities

Laboratory data that are categorical will be summarized using the number and percentage of subjects in the study with the given response at filgotinib baseline and each scheduled postbaseline visit.

The following summaries (number and percentage of subjects) for treatment-emergent laboratory abnormalities will be provided by lab test and treatment group; subjects will be categorized according to the most severe postbaseline abnormality grade for a given laboratory test:

- Graded laboratory abnormalities
- Grade 3 or higher laboratory abnormalities
- Marked laboratory abnormalities

For all summaries of laboratory abnormalities, the denominator is the number of subjects with nonmissing postbaseline values up to 30 days after last dosing date of filgotinib in GLPG0634-CL-205.

A by-subject listing of treatment-emergent Grade 3 or higher laboratory abnormalities and marked laboratory abnormalities will be provided separately by subject ID number and visit in chronological order. These listings will include all test results that were collected throughout the study for the laboratory test of interest, with all applicable severity grades or abnormal flags displayed.

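### No planned ECG table gives the share of treated subjects whose ECG rating ever worsened, and many early-discontinuation ECGs would enter no summary table

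*SAP*

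**What the plan says.** Long-term safety is the primary objective, and Protocol 8.9.1.3 names ECG among its safety domains: "Clinical safety will be evaluated by assessing treatment-emergent AEs (TEAEs), physical examinations, laboratory assessments, ECG results, and vital signs results". The same section adds: "No imputations will be done for safety data in cases where subjects discontinued the study prematurely".

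SAP 7.5.1 plans a shift table in which "ECG results at each visit compared with filgotinib baseline values will be presented by treatment group". The categories are normal, abnormal not clinically significant, abnormal clinically significant, and missing. On percentages it says: "Subjects with a missing value at filgotinib baseline or postbaseline will not be included in the denominator for percentage calculation". Its other output is a listing: "A by-subject listing for ECG assessment results will be provided by subject ID number and visit in chronological order".

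Three further rules decide which ECGs reach a table:

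- SAP 3.5.1 sets the last dose date in the extension to the date of the Final Visit or the EDV.
- SAP 3.5.2 (Table 3-5) gives each visit an 84-day window, from day 7W-40 to day 7W+43 around nominal day 7W+1, applied up to the last dose date. A separate follow-up summary, which includes ECG, runs from last dose + 1 to last dose + 30 days and uses the latest record.
- SAP 3.5.3, for several postbaseline records in one window: "The record closest to the nominal day for that visit will be selected". Worst severity decides only between records on the same selected day.

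For laboratory abnormalities, SAP 7.2.2.3 does otherwise: "subjects will be categorized according to the most severe postbaseline abnormality grade for a given laboratory test".

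**The concern.** A visit table answers how many of those still being assessed are abnormal at that visit. In a study of about 96 months a reader will also want to know how many treated subjects ever moved to a worse ECG rating. No planned table answers that. A subject whose rating worsens and who then leaves is absent from all later visit percentages. One whose rating worsens and recovers is spread over different tables. The visit tables cannot be added up to give a count of subjects.

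The selection rule adds a second loss. The ECG taken at withdrawal is among the more informative ones for safety, yet it competes with the preceding quarterly ECG for a single place in the window and usually loses. Because the EDV date is itself the last dose date, the displaced ECG falls one day short of the follow-up window as well.

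**Working it through.** **Plan's own figure.** The plan gives no ECG rate and no figure for this point. Its one design figure, 0.7 x (595 + 280) = 612.5 (stated as 612), plays no part here.

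**1. Can any planned table yield the ever-worsened share?**

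| Output | Unit | Each subject counted once over all time on treatment? |
|---|---|---|
| Visit shift tables (SAP 7.5.1) | subjects with baseline and that visit | no |
| Follow-up summary (SAP 3.5.2) | subjects with a record 1 to 30 days after last dose | no, one time point |
| Listing (SAP 7.5.1) | individual records | no summary |
| Adverse event tables (SAP 7.1.6.1) | subjects, by preferred term | yes, but for reported events, not ECG ratings |

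**2. How often is the EDV ECG displaced?** Put the quarterly visit k days from nominal, and the EDV on any of the next 84 days with equal probability. The EDV falls in the same window up to nominal + 42 days (7W+43). It loses when it is farther from nominal than |k| days; a tie goes to the later record, the EDV. The losing days are |k|+1 to 42 after nominal, so

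share displaced = (42 - |k|) / 84.

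- k = 0: 42/84 = 50%.
- |k| = 7, the edge of the protocol's visit window: 35/84 = 41.7%.
- k uniform on -7 to +7: mean |k| = 2 x (1 + ... + 7)/15 = 56/15 = 3.73, giving (42 - 3.73)/84 = 45.6%, about 46%.

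Table 3-5 counts from first filgotinib dose, which may be in a core study. The core periods are 12 or 24 weeks, so quarterly visits land near nominal. Any extra drift lowers the share (|k| = 14 gives 28/84 = 33.3%).

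**3. Illustration of visit percentage against ever-affected share.** All rates are assumed. Inputs: 739 subjects (Protocol 8.3.1); 96 x 30.4375/84 = 34.8, so 34 quarterly visits; new clinically significant ECG h = 0.25% or 0.5% per visit; other dropout d = 2% or 4% per visit; between none and all of the affected withdrawing at once; half of the remaining findings resolving by the next visit.

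Ever affected = h(1 - r^34)/(1 - r), with r = (1 - h)(1 - d). For h = 0.005 and d = 0.02: r = 0.9751, r^34 = 0.424, and 0.005 x 0.576/0.0249 = 11.6%.

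| h | d | Ever affected, of 739 | Highest single-visit figure (all withdraw to none withdraw) |
|---|---|---|---|
| 0.25% | 2% | 6.0% (44) | 0.25% to 0.49% |
| 0.25% | 4% | 4.5% (34) | 0.25% to 0.49% |
| 0.5% | 2% | 11.6% (85) | 0.50% to 0.97% |
| 0.5% | 4% | 8.8% (65) | 0.50% to 0.97% |

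The ever-affected share is about 9 to 24 times the highest visit figure.

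**4. The reverse case.** Suppose findings never resolve and nobody withdraws because of them, with h = 0.25% and d = 3%. The last visit table then shows 1 - 0.9975^34 = 8.2%. The share of the 739 ever observed to be affected is 0.0025 x (1 - 0.967575^34)/(1 - 0.967575) = 5.2%. Here the visit table is the larger figure.

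**The case against.** The strongest reply is that affected subjects do not vanish. The Follow-up Visit two weeks after the Final Visit or EDV includes an ECG, and SAP 3.5.2 summarises it. Suppose 0.1% to 0.5% per visit became abnormal, all of them withdrew, nobody else dropped out, the abnormality persisted and everyone attended follow-up. The follow-up summary would then show 1 - 0.999^34 = 3.3% to 1 - 0.995^34 = 15.7%, which is the ever-affected share itself. A reader might infer that the share can appear in no output at all; the documents do not support that. The follow-up summary still misses findings that resolve before that visit, and it depends on attendance. At the Week 156 analysis (SAP 2.4) it cannot cover subjects still on treatment.

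Adverse event capture is also broad. The protocol's definition includes an abnormal finding (8.8.1.2.1.1), investigators judge each ECG for clinical significance (8.8.1.2.5), and events leading to discontinuation have their own table (SAP 7.1.6.1). An ECG finding that causes withdrawal is thus likely to be counted. But neither document ties a clinically significant rating to an adverse event entry, and the tables run by preferred term.

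Displacement of the EDV ECG matters only when the worsening first appears there. If it was already present at the quarterly visit, that record is kept.

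Finally, the protocol does not promise a worst-value ECG analysis, the study is descriptive, and Protocol 6.5 reports no clinically relevant ECG effect in Phase 1 and 2. These points stand and limit the weight of the concern. They do not supply the missing summary.

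**Conclusion.** The point holds as a gap in reporting. No planned table gives the share of treated subjects whose investigator ECG rating ever worsened from filgotinib baseline. In addition, about 46% of EDV ECGs (50% if every quarterly visit falls on its nominal day) would enter neither a visit table nor the follow-up summary. That figure follows from the SAP's rules, given uniform withdrawal times and quarterly visits within 7 days of nominal.

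A reader might infer that the visit tables are biased in the drug's favour. The documents do not support a direction: the tables understate the ever-affected share when abnormalities resolve or lead to withdrawal, and can exceed it when abnormalities persist in those who stay. Nor should 4.5% to 11.6% be read as an expected rate. It rests wholly on assumed inputs and shows only how far a visit percentage and an ever-affected share can differ.

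This is a cheap improvement that should be made, not a defect that undermines the study.

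**What to change.** Add to SAP 7.5.1 a shift table from filgotinib baseline to each subject's worst postbaseline investigator ECG rating. Use every scheduled, unscheduled, EDV and Follow-up ECG up to 30 days after the last filgotinib dose, and count each subject once. The denominator is Safety Analysis Set subjects with a baseline ECG and at least one postbaseline ECG. This brings the displaced EDV records into a summary and matches the cutoff already used for laboratory abnormalities.

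Show the table beside exposure, because a worst-value percentage rises with length of follow-up. Keep the by-visit tables as supportive.

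The cost is one paragraph and one table, with no new data collection. SAP 7.3 has the same by-visit form for vital signs ("Change from filgotinib baseline at each postbaseline visit"). A per-subject maximum change could be added there, but it is secondary and this point does not depend on it.

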7.6. Other Safety Measures

A data listing will be provided for subjects who have positive or borderline urine or serum pregnancy test result during the study.

7.7. Changes From Protocol-Specified Safety Analyses

There are no deviations from the protocol-specified safety analyses.

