The following decision choice will be used by the investigator to describe the causality assessment between the reported event and the investigational medicinal product.

- Unrelated: No relationship between the AE and the administration of investigational product; related to other etiologies such as concomitant medications or subject's clinical state.
 - Unlikely: Event or laboratory test abnormality, with a time to study medication intake that makes a relationship improbable (but not impossible). Disease or other drugs provide plausible explanations.
 - Possible: Event or laboratory test abnormality, with reasonable time relationship to study medication intake which could also be explained by disease or other drugs. Information on drug withdrawal may be lacking or unclear.
 - Probable: Event or laboratory test abnormality, with reasonable time relationship to study medication intake. Event unlikely to be attributed to disease or other drugs. Response to withdrawal is clinically reasonable and rechallenge not required.
-

- Certain: Event or laboratory test abnormality, with plausible time relationship to study medication intake which cannot be explained by disease or other drugs. Response to withdrawal is plausible (pharmacologically, pathologically). Event definitive pharmacologically or phenomenologically (ie, an objective and specific medical disorder or a recognized pharmacological phenomenon). Rechallenge satisfactory, if necessary.

Action Taken Regarding Investigational Product

The action taken must be described by choosing among:

- Dose not changed: In case no action is taken regarding the study medication.
- Study medication permanently withdrawn: In case a subject is permanently withdrawn from the study.
- Study medication temporarily withdrawn: In case the study medication is temporarily withdrawn.
- Dose reduction: If a subject's daily dose is adjusted from 200 mg to 100 mg (q.d., once daily in the morning).
- Not applicable: Other situations (eg, in case an AE started after the last study medication administration).

Outcome

Each AE must be rated by choosing among:

- Recovered/Resolved.
- Recovered/Resolved with sequelae.
- Not recovered/Not resolved.
- Fatal.
- Recovering/Resolving.
- Unknown.

8.8.1.2.1.2 Recording Adverse Events

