8.8.1.2.5 Other Safety Assessments

12-Lead ECG

A resting 12-lead ECG will be performed at times presented in the flow chart.

Subjects should rest for at least 5 minutes in the supine position before ECG evaluation.

Parameters to be recorded in the eCRF include: HR, RR, QRS, uncorrected QT, morphology, and rhythm analysis. QTcF will be derived during the statistical analysis. ECGs will be interpreted by the investigator for clinical significance and results will be entered into the eCRF.

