7.1.6.1. Summaries of AE incidence in Combined Severity Grade Subsets

The number and percentage of subjects who experienced at least 1 TEAE will be provided and summarized by SOC, HLT, PT, and treatment group. For other AEs described below, summaries will be provided by SOC, PT, and treatment group:

- TEAEs of Grade severe
- TEAEs of Grade moderate or higher
- All TE treatment-related AEs
- TE Treatment-related AEs of Grade severe
- TE Treatment-related AEs of Grade moderate or higher
- All TE SAEs
- All TE treatment-related SAEs
- All TEAEs leading to premature discontinuation of any study drug
- All TEAEs leading to premature discontinuation of study
- All TEAEs leading to temporary interruption of any study drug
- All TE SAEs leading to death (ie, outcome of death)

A brief, high-level summary of AEs described above will be provided by treatment group and by the number and percentage of subjects who experienced the above AEs. All deaths reported in the study will be also included in this summary.

Multiple events will be counted only once per subject in each summary. Adverse events will be summarized and listed first in alphabetic order of SOC and HLT within each SOC (if applicable), and then by PT in descending order of total frequency within each SOC. For summaries by

severity grade, the most severe grade will be used for those AEs that occurred more than once in an individual subject during the study.

In addition to the above summary tables, all TEAEs and TE treatment-related AEs will be summarized by PT only, in descending order of total frequency.

In addition, data listings will be provided for the following:

- All AEs, indicating whether the event is treatment emergent
- All AEs of Grade severe
- All AEs of Grade moderate or higher
- SAEs
- Deaths
- All SAEs leading to death (ie, outcome of death)
- AEs leading to premature discontinuation of any study drug
- AEs leading to premature discontinuation of study
- AEs leading to temporary interruption of any study drug

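### SAP 7.7 declares no departure from the protocol's safety analyses, yet the SAP omits ECG interval and QTcF summaries, a table of TEAEs leading to dose reduction, and by-visit numeric summaries of 21 blood tests

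*SAP*

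**What the plan says.** SAP 7.7 is one sentence: "There are no deviations from the protocol-specified safety analyses".

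The protocol's commitments are in 8.9.1.3 (Safety Variables) and 8.8.1.2.5 (Other Safety Assessments):

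- **Numeric summaries.** "Original results and changes from baseline will be summarized for all laboratory, vital signs, and ECG parameters".
- **AE tabulations.** For TEAEs, "relationship to study medication, dose reductions, and temporary/permanent treatment stops will all be tabulated".
- **ECG.** The eCRF captures "HR, RR, QRS, uncorrected QT, morphology, and rhythm analysis", and "QTcF will be derived during the statistical analysis".

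The corresponding SAP text is narrower:

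- **ECG (7.5).** The only subsection is 7.5.1, a shift table in which the investigator's "assessment of ECG results at each visit compared with filgotinib baseline values will be presented by treatment group", using normal/abnormal categories, plus a by-subject listing of that assessment.
- **AEs by action taken (7.1.6.1).** Tables and listings cover premature discontinuation of drug, premature discontinuation of study, and interruption ("All TEAEs leading to temporary interruption of any study drug"). Dose reduction is not among them.
- **Laboratory (7.2.1).** By-visit descriptive statistics and changes are given for an enumerated list of tests, shorter than the list in Protocol 8.8.1.2.2.

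**The concern.** The primary objective is long-term safety and tolerability, so the safety outputs are the main product of this study. A section recording changes from protocol is useful only if it is accurate. Here it tells the reader that the SAP delivers everything the protocol specified, when a programmer following the SAP would produce no ECG interval or QTcF summary and no dose-reduction TEAE table. SAP section 1 sends only changes made after SAP finalization to the CSR, so omissions already in the SAP would not be picked up there either.

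Two of the gaps bear on specific questions:

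- **Tolerability.** The protocol allows dose reduction for intolerance or safety reasons, so TEAEs leading to it measure tolerability directly.
- **Continuity with the core studies.** Protocol 6.4 reports lymphocyte-subset, free-testosterone and prolactin results from CL-203, and 6.5 repeats the subset finding. The SAP plans no by-visit summary of subsets or prolactin that would extend those statements to long-term treatment, and it does not say which testosterone it means.

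**Working it through.** The documents give no count of omitted analyses, so there is no stated figure to reproduce. The check is an item-by-item comparison.

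**1. ECG**

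Numeric parameters under Protocol 8.8.1.2.5: HR, RR, QRS and QT (4 recorded) + QTcF (1 derived) = 5.

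SAP 7.5 plans a by-visit value or change for 0 of the 5. RR, QRS, QT and QTcF appear nowhere in the SAP. Pulse is summarized in SAP 7.3, but as a vital sign rather than ECG heart rate. SAP 3.5.2 says follow-up ECG data will be summarized but names no parameter.

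**2. TEAEs by treatment change**

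| Named in Protocol 8.9.1.3 | Table in SAP 7.1.6.1 |
|---|---|
| Permanent stop | Yes |
| Temporary stop | Yes |
| Dose reduction | No |

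So 2 of 3 are covered. Dose reduction has its own action-taken category in Protocol 8.8.1.2.1.1, used where the subject's "daily dose is adjusted from 200 mg to 100 mg", and it is separate from temporary withdrawal. The interruption table therefore does not absorb it.

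No other SAP output fills the gap. SAP 3.2 pools 100 mg q.d., 100 mg b.i.d. and 200 mg q.d. within each of its two groups, and SAP 4.2 summarizes exposure by duration only.

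**3. Laboratory**

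Tests in Protocol 8.8.1.2.2 compared with the list in SAP 7.2.1:

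| Class | Protocol tests | Absent from SAP 7.2.1 | Number absent |
|---|---|---|---|
| Chemistry and lipids | 22 | BUN, GGT, amylase, lipase, albumin, total protein, sodium, potassium, chloride, uric acid, calcium, phosphorus | 12 |
| Hematology and coagulation | 18 (WBC differential taken as five cell types) | CD3, CD19, CD4, CD8, CD3-/CD16+, CD56+, aPTT, PT | 8 |
| Male hormones | 6 | Prolactin | 1 |

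Chemistry check: 22 − 10 in the SAP (ALT, AST, ALP, total bilirubin, creatinine, glucose, triglycerides, total cholesterol, HDL, LDL) = 12.

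Total: 12 + 8 + 1 = 21.

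The total depends on how tests are counted:

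- CD3-/CD16+ and CD56+ taken as one marker: 21 − 1 = 20.
- Free testosterone counted as omitted, because the SAP lists only testosterone: 21 + 1 = 22.
- The six urinalysis items added as well: 22 + 6 = 28.

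**4. What the SAP still provides for the omitted tests**

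SAP 7.2 gives by-subject listings for hematology, serum chemistry and urinalysis, with flags. SAP 7.2.2.3 gives graded treatment-emergent abnormalities by laboratory test, without restriction to the 7.2.1 list, and summarizes categorical laboratory data by visit. These are not values and changes from baseline for each parameter. The listing sentence in 7.2 does not name hormones.

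**The case against.** The strongest objections are these.

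- **The protocol does not say by-visit or numeric.** Protocol 8.9.1.3 requires results and changes to be summarized, and the ECG shift table and graded laboratory tables are summaries relative to baseline. This has some force for the laboratory tests, where coverage is reduced rather than absent. It does not rescue the ECG: a shift in an overall normal/abnormal reading gives neither the value nor the change of any interval, and QTcF is not derived at all.
- **The count of 21 is a convention.** This stands. It covers blood tests only, treats the six subsets as six tests, and takes the SAP's testosterone entry as sufficient. Other conventions give 20 to 28. None brings the omission near zero.
- **The SAP was written against Amendment 3, and the protocol supplied is Amendment 4.** The visible Amendment 4 changes concern the DSMB text, a discontinuation criterion and packaging, and touch neither 8.9.1.3 nor 8.8.1.2.5. Part of the change log is not available, so identity of the safety text across the two versions is likely but not proven.
- **Serum chemistry in the listing may be meant to include hormones.** It may. The hormone-listing point is minor and needs only a clarifying word.
- **All analyses are descriptive and the data are collected regardless.** True: no endpoint, analysis set or inference changes. That limits the severity, but it does not make the statement in 7.7 correct.

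A SAP may narrow what a protocol promised. Section 7.7 is where it should say so, and it says the opposite.

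**Conclusion.** The concern holds. Against the protocol supplied, the no-deviation statement in SAP 7.7 is incorrect.

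Two omissions are clear: no numeric ECG summary (0 of 5 parameters, including QTcF) and no dose-reduction TEAE table or dedicated listing (2 of the 3 named treatment changes covered). The third is partial: 21 protocol blood tests have no by-visit numeric summary, although the hematology and chemistry tests among them are still listed and may appear in graded tables.

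The conclusion assumes that Amendment 3 carried the same safety text as Amendment 4. The figure of 21 rests on the counting convention in the working. The matter should be corrected because safety is the primary objective, but it does not threaten the validity of any planned test.

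**What to change.** Amend the SAP as follows. For each of the first three items the alternative is to leave the analysis out and declare the omission in 7.7.

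1. **7.5:** add by-visit values and change from filgotinib baseline for HR, RR, QRS, QT and derived QTcF.
2. **7.1.6.1:** add a summary and a listing of TEAEs leading to dose reduction, using the existing action-taken field.
3. **7.2.1 and 7.2:** add the remaining protocol laboratory tests; state whether testosterone is total, free or both; name hormones in the by-subject listing.
4. **7.7:** replace the present sentence with a correct one, giving each deliberate omission and its reason.

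Items 1 and 2 come first; item 3 is secondary given the partial coverage. The cost is SAP wording and standard descriptive tables from data the protocol already collects in the eCRF or at the central laboratory. No new assessments are needed.
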